9.3 Selection of Study Population

At least 850 subjects with EAD including MCI due to AD and the early stages of mild AD will be enrolled across up to approximately 250 centers worldwide (revised per Amendment 06). Randomization will be stratified according to region (7 levels), clinical dementia staging, with no more than approximately 25% of the randomized subjects diagnosed with the early stages of mild dementia due to AD, and concurrent AD medication use. (revised per Amendments 01 and 02) Subjects who do not meet all of the inclusion criteria or who meet any of the exclusion criteria will not be eligible to receive study drug.

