7. Subjects must have been on stable doses of all other (ie, non-AD related) permitted concomitant medications for at least 4 weeks before Randomization, except for medications which are administered as short courses (eg, up to 3 weeks unless discussed and agreed with the medical monitor) of treatment (eg, anti-infectives, oral steroids) or which are to be used on a Pro re nata (PRN) basis. Subjects who require a short course of treatment, such as anti-infectives or oral steroids, may be randomized once the acute illness has completely resolved, even if the concomitant medication continues. (revised per Amendment 01)
8. Must have an identified study partner (defined as a person able to support the subject for the duration of the study and who spends at least 8 hours per week with the subject). The study partner must be literate and able to provide written informed consent. (revised per

Amendment 04) In addition, this person must be willing and able to provide follow-up information on the subject throughout the course of the study. This person must, in the opinion of the investigator, spend sufficient time with the subject on a regular basis such that they can reliably fulfill the requirements of being a study partner. A study partner need not be living in the same residence with the subject. For such a study partner not residing with the subject, the investigator has to be satisfied that the subject can contact the study partner readily during the times when the study partner is not with the subject. Study partners need to provide input to the following assessments: CDR, FAQ, EQ-5D, QOL-AD, Zarit's Burden Interview, NPI-10, and the clinical assessment of suicidality. (revised per Amendment 01) Consideration can occur for the investigator to decide whether the study partner can provide information over the telephone or whether the study partner must attend the study visits in person with the subject.

9. Provide written informed consent. Subjects must, in the investigator's judgment, have the capacity to consent (capacity to consent should be determined in accordance with applicable professional standards and local laws/regulations). (revised per Amendment 04)

For inclusion criteria specific to the Extension Phase, refer to [Appendix 5 in Section 12](#).

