 - Psychiatric diagnosis or symptoms, (eg, hallucinations, major depression, or delusions) that, in the opinion of the investigator, could interfere with study procedures
 - Has a “yes” answer to C-SSRS suicidal ideation items 4 or 5, or any suicidal behavior within 6 months before Screening, at Screening, or at the Randomization Visit, or has been hospitalized or treated for suicidal behavior in the past 5 years before Screening
 7. Have any contraindications to MRI scanning, including cardiac pacemaker/defibrillator, ferromagnetic metal implants (eg, in skull and cardiac devices other than those approved as safe for use in MRI scanners) or
 - Have any evidence of other clinically significant lesions that could indicate a dementia diagnosis other than AD on brain MRI at Screening.
 - Exhibit other significant pathological findings on central read of the brain MRI at Screening, including but not limited to: an area of superficial siderosis; evidence of cerebral vasogenic edema; evidence of cerebral contusion, encephalomalacia, aneurysms, vascular malformations, or infective lesions; evidence of multiple infarcts; evidence of stroke involving a major vascular territory; severe small vessel or diffuse white matter disease as defined by a score of 3 on the age-related white matter changes score ([Wahlund, et al., 2001](#)); space occupying lesions; or brain tumors (however, lesions diagnosed as meningiomas or arachnoid cysts and less than 1 cm at their greatest diameter need not be exclusionary). (revised per Amendments 04 and 06)
 8. Subjects who have a history of moderate to severe hepatic impairment (eg, Child-Pugh Class B or C). Any 2 of the following criteria at Screening would exclude the subject: $\text{INR} \geq 1.7$; $\text{bilirubin} \geq 1.5 \times \text{ULN}$; $\text{albumin} < \text{LLN}$; ascites or hepatic encephalopathy. Please note that a single significant abnormality could meet criteria for moderate impairment. (revised per Amendment 02)

9. Results of laboratory tests conducted during Screening that are outside the following limits:

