- Absolute lymphocyte count (ALC) below Lower Limit of Normal (LLN) or below 800 per mm³ (whichever is higher); ALC will be derived from the complete blood count (CBC) with differential representing the normal lymphocytes (with atypical lymphocytes removed and presented as a separate count if they are present) and calculated by the white blood cell count × percentage of lymphocytes. (revised per Amendments 01 and 02)
- Thyroid stimulating hormone (TSH) above normal range. Other tests of thyroid function with results outside the normal range should only be exclusionary if they are considered clinically significant by the investigator (this applies to all subjects whether or not they are taking thyroid supplements)
- Abnormally low (below LLN) serum Vitamin B12 levels (if subject is taking Vitamin B12 injections, level should be at or above the LLN). Levels of Vitamin B12 may be confirmed with reflex testing to include methylmalonic acid (MMA) analysis, if available in region. (revised per Amendment 06)

10. Subjects at risk of increased risk of infection, specifically:

- Subjects with chronic viral hepatitis. Subjects with a history of chronic viral hepatitis C may be included if they meet the following requirements:
 - 1) evidence of treatment with direct antiviral combination therapy
 - 2) evidence of sustained virological response at least 12 weeks post-treatment

The inclusion of subjects with a history of chronic viral hepatitis C must be discussed and agreed with the medical monitor. (revised per Amendment 04)

- A history of active tuberculosis disease (TB), a history of ophthalmic shingles or a history of ocular herpes simplex virus (HSV) infection (revised per Amendment 04)
- Any active infection within the last 4 weeks before randomization. For such cases, the timing of randomization can be extended (up to 4 weeks) to allow the infection to resolve
- Any immunological disease which is not adequately controlled, or which requires treatment with biologic drugs during the study. History of immunoglobulin deficiency or other immunodeficiency disorders (including subjects known to be HIV positive)

11. Have received any live vaccine/live attenuated vaccine in the 3 months before randomization (revised per Amendment 01)

12. Any chronic inflammatory disease that is not adequately controlled or that requires systemic immunosuppressive or immunomodulatory therapy. (revised per Amendment 04)

NOTE: The following subjects do not need to be excluded:

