- q: Study-eligible subjects from select geographical sites (based on proximity to the tau PET ligand manufacturing sites) in the US who have an amyloid positive study-specific PET scan and consent to participate in the amyloid PET substudy will also be offered participation in a third optional longitudinal substudy (tau PET substudy). Tau PET scanning will be performed using a sponsor-supplied tau PET imaging agent, eg PI-2620. Participation in the tau PET substudy is optional and will require specific consent that will not affect enrollment or treatment in the main study or participation in the amyloid PET or CSF substudies. Subjects who participate in the optional longitudinal tau PET substudy will have up to 14 days to be randomized into the study from the reporting of the last screening eligibility assessment in order to accommodate the additional tau PET scan required pre-randomization. There must be at least 48 hours between the tau PET scan and randomization. If the subject has also consented to participate in the longitudinal CSF substudy, there must be at least 48 hours between each procedure (amyloid PET scan, tau PET scan and CSF collection) and between the last procedure and randomization. Only those subjects who have a study-specific amyloid positive PET scan and who have consented to both amyloid and tau PET substudies will be administered the tau PET tracer and scanned. (revised per Amendment 05)

Table 5 Schedule of Procedures/Assessments in Study E2609-G000-301 (Revised per Amendments 05 and 06)

Phase Period	Randomization												Follow-Up			UNS Visit ^d
	Treatment												ED ^b	14 ^c	15 ^c	
Visit ^a	2	3	4	5	6	7	8	9	10	11	12	13	ED ^b	14 ^c	15 ^c	
Day	1	15	29	57	85	183	274	365	456	547	638	729		757	813	
Week	1	3	5	9	13	27	40	53	66	79	92	105		109	117	
Weeks elapsed since 1st dose	0	2	4	8	12	26	39	52	65	78	91	104		108	116	
Nominal months elapsed since 1st dose	0		1	2	3	6	9	12	15	18	21	24		25	27	
Procedures/ Assessments																
Consent (subject and study partner)																X ^{dd}
Routine physical examination with dermatologic review	X	X	X	X	X	X	X	X	X	X	X	X	X	X	X ^c	X
Inclusion and Exclusion criteria	X														X ^{dd}	
Vital signs and respiratory rate ^f	X	X	X	X	X	X	X	X	X	X	X	X	X	X	X ^c	X
Weight	X				X	X	X	X	X	X	X	X	X		X	X
Neurologic examination ^g					X	X		X		X		X	X		X	X
Concomitant medications ^h	X	X	X	X	X	X	X	X	X	X	X	X	X	X	X	X
Single 12-lead ECG ⁱ	X		X		X	X		X		X		X	X	X	X ^c	X

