Blood samples for PK ^w		X	X		X	X		X		X		X	X			
Blood samples for PD and exploratory biomarkers ^x	X	X	X		X	X		X		X		X	X	X	X	
CSF sampling for PK and PD (optional substudy) ^y												X	X		X ^{cc}	
Adverse events ^{ff}	X	X	X	X	X	X	X	X	X	X	X	X	X	X	X	X
Sleep/Dream Questionnaire ^z	X	X	X	X	X	X	X	X	X	X	X	X	X	X	X	X
Possible Drug Abuse Potential Form/ Questionnaire ^{aa}	X	X	X	X	X	X	X	X	X	X	X	X	X	X	X	X
Randomization	X															
Dispense study drug	X ^b b	X	X	X	X	X	X	X	X	X	X				X ^{dd}	

Table 5 Schedule of Procedures/Assessments in Study E2609-G000-301 (Revised per Amendments 05 and 06)

Phase	Randomization														
	Treatment												Follow-Up		
Period	2	3	4	5	6	7	8	9	10	11	12	13	ED ^b	14 ^c	15 ^c
Visit ^a															
Day	1	15	29	57	85	183	274	365	456	547	638	729		757	813
Week	1	3	5	9	13	27	40	53	66	79	92	105		109	117
Weeks elapsed since 1st dose	0	2	4	8	12	26	39	52	65	78	91	104		108	116
Nominal months elapsed since 1st dose	0		1	2	3	6	9	12	15	18	21	24		25	27
Procedures/ Assessments															

Notes:

ADAS-cog14 = Alzheimer’s Disease Assessment Scale - Cognitive subscale (14 items), AE = adverse event, CBP = child-bearing potential, CDR = Clinical Dementia Rating scale, CMV = cytomegalovirus, CNS = central nervous system, CSF = cerebrospinal fluid, C-SSRS = Columbia Suicide Severity Rating Scale, ED = Early Discontinuation, EQ-5D = EuroQol-5 Dimensions, FAQ = Functional Assessment Questionnaire (also known as the Functional Activities Questionnaire), fMRI = functional MRI (to be performed task free at resting state), HSV1 = herpes simplex virus 1 (orolabial herpes), HSV2 = herpes simplex virus 2 (genital herpes), INR = International Normalized Ratio, LP = lumbar puncture, MMSE = Mini Mental State Examination, MRI = magnetic resonance imaging, NPI = Neuropsychiatric Inventory, PBMC = peripheral blood mononuclear cell, PD = pharmacodynamics, PET = positron emission tomography, PK = pharmacokinetics, QOL-AD = Quality of Life in Alzheimer’s Disease, QTcF = QTc interval calculated using Fridericia’s formula, UNS = unscheduled, vMRI = volumetric MRI.

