reported during the first 4 weeks following the last dose of study drug that might indicate physical dependency also require a more detailed follow-up through completion of the same eCRF form. Categories and examples of AEs indicating signals of possible drug abuse are provided in [Appendix 3](#) and a more comprehensive list is provided in the eCRF Completion Guidelines. (revised per Amendments 02 and 04)

- bb: The first dose of study drug will be given to the subject at the study site. Subjects will be encouraged to stay at the site for observation for at least 30 minutes following their first dose of study drug. The duration of this observation period can be extended at the investigator’s discretion, eg, if warranted by medical history or concomitant medication. (revised per Amendment 04) Visit 2 bottles are re-dispensed at Visit 3 after accountability is performed. (revised per Amendment 06)
- cc: Only for Extension Phase subjects who did not participate in optional longitudinal substudies in the Core Study but who wish to consent to optional longitudinal substudies in the Extension Phase
- dd: For subjects entering the Extension Phase only
- ee: Immunological assessments only required for subjects randomized before 07 Sep 2018
- ff: New AEs will be collected for 4 weeks post last dose and followed-up for 12 weeks, or until resolution, whichever comes first. If >4 weeks post last dose, AEs relating to study procedures will be collected only
- gg: C-SSRS to be completed if any positive responses from the Clinical Assessment of Suicidal Thinking and Behavior
- hh: For those subjects entering the Extension Phase, NPI-12 will be used if available and both NPI-10 and NPI-12 scores calculated.
- ii: Not required for those entering Extension Phase

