Appendix 5 Open-label Extension Phase (revised per Amendment 06)

Primary Objective

- To evaluate the long-term safety and tolerability of daily dosing with elenbecestat in subjects with Early Alzheimer's Disease (EAD)

Secondary Objectives

- To evaluate the long-term effects of elenbecestat on Clinical Dementia Rating –Sum Of Boxes (CDR-SB), Alzheimer's Disease Composite Score (ADCOMS), Mini Mental State Examination (MMSE), Functional Assessment Questionnaire (FAQ), Alzheimer's Disease Assessment Scale - cognitive subscale (ADAS-cog14), and ADAS-cog14 Word List (immediate recall and delayed recall)
- To evaluate the time to conversion to dementia for subjects who were not clinically staged as having dementia at Core Study baseline, based on clinical diagnosis
- To evaluate whether the treatment benefit of elenbecestat at the end of the Core Study is maintained over time in the Extension Phase

Biomarker Objectives

- To evaluate the long-term effect of elenbecestat on brain amyloid and tau levels as measured by positron emission tomography (PET) (optional substudies)
- To evaluate the long-term effect of elenbecestat on hippocampal atrophy as measured by changes in hippocampal volume using volumetric magnetic resonance imaging (vMRI)
- To evaluate the long-term effect of elenbecestat in preserving brain connectivity as measured by task-free functional magnetic resonance imaging (fMRI)
- To evaluate the long-term effect of elenbecestat on cerebrospinal fluid (CSF) t-tau, phosphorylated-tau (p-tau), and amyloid beta (A β) levels (optional substudy)
- To evaluate the long-term effect of elenbecestat on plasma amyloid (eg, A β (1-x)) levels
- To explore the long-term effect of elenbecestat on potential plasma and CSF biomarkers of AD (eg, neurofilament (NFL), visinin like protein 1 (VILIP1), human cartilage glycoprotein-39 (YKL-40), and neurogranin [Ng])

Exploratory Objectives

- To explore the long-term effect of elenbecestat on the initiation or dose increase of other Alzheimer's disease (AD) pharmacotherapies
- To explore the long-term effect of elenbecestat on the Neuropsychiatric Inventory (NPI)-10 and if available NPI-12

Eligibility Criteria

Subjects who do not meet all of the inclusion criteria will not be eligible to receive study drug.

Inclusion:

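### Table 5 requires an exclusion check when Extension drug is dispensed at Visit 15, but Appendix 5 has no exclusion criteria, so a first dose is allowed at a known ALC below 800/mm3

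*Protocol*

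**What the plan says.** In Protocol Section 9.5.2.1, Table 5 marks the rows "Inclusion and Exclusion criteria" and "Dispense study drug" in the Visit 15 column. Both marks carry footnote dd, "For subjects entering the Extension Phase only". Appendix 5 treats Visit 15 as Day 1 of the Extension.

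Appendix 5 gives three inclusion criteria: Core completion with Visit 15 no more than 4 weeks before the start, consent with capacity, and a study partner. It gives no exclusion criteria, and its drug rule is "Subjects who do not meet all of the inclusion criteria will not be eligible to receive study drug". The matching Core sentence in Section 9.3 also covers those "who meet any of the exclusion criteria will not be eligible to receive study drug".

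Section 9.3.1 points onward: "For inclusion criteria specific to the Extension Phase, refer to" Appendix 5. Section 9.3.2 (exclusions) never mentions the Extension. Its ALC limit sits under item 9, "Results of laboratory tests conducted during Screening that are outside the following limits". Items 10 and 11 count the 4-week infection limit and the 3-month live-vaccine limit back from randomization.

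Section 9.3.3 interrupts drug after a confirmed ALC below 800/mm3 and allows a restart only above that value. Appendix 5 imports 9.3.3 as grounds for discontinuing open-label drug. For a low ALC at Visit 14 or 15, Section 9.5.1.5.1 and Table 5 footnote c require retesting every 4 weeks.

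**The concern.** A site at Visit 15 is told to check exclusions that the Extension appendix does not contain, and then to dispense. The check matters because it comes after 12 weeks off drug and, for former placebo subjects, immediately before first exposure. Section 7.1 reports some CD4 reduction at 50 to 100 mg in the multiple-dose study, and the Core entry limits on ALC, infection and live vaccines address that kind of risk. Sites remain blinded through Follow-up (Section 9.4.6), so they cannot take extra care only with former placebo subjects; one rule must serve all entrants. Safety is the Extension's primary objective. What is at stake is avoidable dosing in a state where the plan itself would not restart drug, and inconsistent entry decisions between sites.

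**Working it through.** The plan gives no figure to reproduce. The check sets the rules side by side and adds some date arithmetic.

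**Reading A: Section 9.3.2 does not apply to the Extension.** Only the three inclusion criteria bind. None concerns ALC, infection, vaccines or medication, so the exclusion half of the Table 5 check has no content.

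**Reading B: Section 9.3.2 applies at Visit 15.** Item 19 excludes anyone who took part in an elenbecestat study, which is every entrant. With item 19 set aside, the relevant limits fall as follows:

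| Rule | Anchor | Reaches Extension Day 1? |
|---|---|---|
| ALC, item 9 | Screening tests | No |
| Active infection within 4 weeks, item 10 | Randomization | No |
| Live vaccine within 3 months, item 11 | Randomization | No |
| Immunosuppressant washout, Section 9.4.7(b) | Randomization | No |
| Same washout, Appendix 2 Listing 2 | Baseline | Arguably yes: Visit 15 is the Extension baseline |
| Examination or vital-sign findings, item 13 | Screening or Baseline | Arguably yes |
| Uncontrolled conditions, items 10, 12, 13; prohibited medication, item 18 | Undated | Yes |

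**Low ALC.** Section 9.3.3 speaks of interrupting and restarting, which presupposes dosing under way. Its Extension rule for two occurrences counts from Visit 16. Retesting under footnote c carries no hold on dispensing. A first dose below 800/mm3 is therefore not forbidden, while a restart is.

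**Dates (Table 5).**
- Off-drug gap, Visit 13 to Visit 15: 813 − 729 = 84 days (81 to 87 with the ±3-day Follow-up window).
- Retest after a low ALC at Visit 14: 757 + 28 = Day 785. At Visit 15 that result is 813 − 785 = 28 days old. Visit 15 blood goes to a central laboratory, so its result may not be back at same-day dispensing; the known value is then Visit 14 or its retest.
- If such a subject is dosed at Visit 15 and the ALC is again low, dosing lasts until the repeat confirms it. Assuming 1 to 3 days per laboratory result, and 0 to 5 days to redraw (Section 9.3.3): minimum 1 + 0 + 1 = 2 days, maximum 3 + 5 + 3 = 11 days.
- Live vaccine, taking 3 months as 91 days: 91 > 87, so any live vaccine in the gap falls inside a Core-length washout counted back from Visit 15. With the full 4-week delay, one given in the last 91 − 28 = 63 days before Visit 15 still does.

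**The case against.** The strongest reply is that a sensible site would read the protocol protectively. Section 9.3.2 has no Core subheading, Section 9.3 bars drug for anyone meeting an exclusion, and nobody would use item 19 to void the whole Extension. The undated items then bar ongoing prohibited therapy and uncontrolled disease, and item 13 can reach an active infection. A count that is low at Visit 14 and again near Day 785 is in substance confirmed, so dispensing into it strains Section 9.3.3.

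Much of this stands as mitigation. Appendix 5 also shuts out Core drug discontinuers, which removes subjects stopped for repeated confirmed lymphocytopenia, seizures, hepatic impairment, suspected drug rash or unresolved severe infection. Visit 15 includes physical examination, vital signs, ECG and hematology for entrants, and Table 9 repeats hematology at weeks 2, 4 and 8. Section 7.1 describes lymphocyte effects resolving by 21 days after the last dose, so carry-over at 84 days is unlikely.

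It does not supply the missing rule. Each argument needs the site to choose which Core items to keep and to re-date them itself, and none states a hold on the first dose.

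A reader might infer that no immunosuppressant washout exists for the Extension. The documents do not support that: Section 9.4.7 and Listing 2 disagree on the anchor, and the Listing 2 anchor can be read to reach Visit 15. Inclusion criterion 7 also lets the Core accept short courses such as oral steroids, so not every such exposure was meant to be kept apart from drug.

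**Conclusion.** The inconsistency is real, and its clearest consequence is that a first Extension dose is permitted at a known ALC below 800/mm3 where a restart is not. Severity is minor to moderate. Falls to near or below the lower limit of normal were described at 200 and 400 mg, not at the 50 mg used here. On the turnaround assumption above, dosing in a persistently low state would be caught within about 2 to 11 days. The protocol gives no basis for the number of subjects affected. Core primary and key secondary analyses do not change.

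A reader might take the 84-day gap and the washout lengths as a measure of risk, or conclude that all Section 9.4.7 prohibitions should run through Follow-up. Neither follows. The day counts are calendar time, not event rates. The documents show no problem with CES2 inhibitors, which need only 5 half-lives or 7 days. A 6-month biologic washout could not clear within the entry window, so imposing it is a separate trade-off.

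Confidence is moderate. The Amendment 06 synopsis and Table 9 footnote m were not available to read, and either might add a rule, although dispensing at Visit 15 itself is governed by Table 5.

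**What to change.** Amend the protocol as follows.

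1. In Appendix 5, bar the first Extension dose while the most recent available ALC (Visit 14 or its retest) is below 800/mm3, or while a severe or active infection or moderate to severe hepatic impairment is unresolved. Let the 4-week entry window serve this hold. Section 9.1 already allows later entry without giving a reason; only Appendix 5 links it to consent. The Core has the same device for infection in item 10: "For such cases, the timing of randomization can be extended (up to 4 weeks) to allow the infection to resolve".
2. In the Appendix 5 drug rule, restore the Core limb covering those "who meet any of the exclusion criteria will not be eligible to receive study drug". State which Section 9.3.2 items apply at Visit 15, with dates counted back from Extension Day 1, including the live-vaccine limit. State that item 19 does not apply to Core participation.
3. Align the immunosuppressant washout in Section 9.4.7 and Listing 2 to Extension Day 1 for entrants, keeping the Core short-course exception.

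Do not extend the CES2-inhibitor ban, or prohibitions a to d as a block, through Follow-up.

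The cost is amendment wording and perhaps one extra dispensing contact for a held subject. A few entrants start later. One whose condition or washout outlasts the 4-week window becomes ineligible, for example after a live vaccine in the 63 days before Visit 15, so intending entrants should be told in advance. The 800/mm3 limit is the existing restart threshold, so nothing stricter is introduced.
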